In summary, anodal tDCS targeting M1 will be selected since this approach influences sensational components of pain perception. BreESTim is shown to modulate the affective component of pain perception. Therefore, we expect that that combined BreESTim and tDCS treatment has addictive analgesic effects as compared to BreESTim or tDCS alone. We will test this treatment in healthy subjects and for neuropathic pain management in common patient populations, such as brain injury (BI), spinal cord injury (SCI), and amputation.

4. Description of Study:

This study has 4 experiments. The main idea is to test the effectiveness of the new intervention for neuropathic pain management for healthy subjects and one patient population (SCI, BI, or amputation) in each experiment. We request to recruit 20 subjects (5 subjects each group for healthy, SCI, BI and amputation). Overall, We plan to adopt recently published BreESTim (Li et al. 2013) and tDCS(Boggio et al. 2008) research protocols in this experiment. Briefly, this will be a single-center, randomized, cross-over trial to determine whether there is additive analgesic effect of a single session of combined and BreESTim and tDCS stimulation in healthy, and other patient subjects.

[figure not shown]
Subject recruitment

A total of 20 patients is planned to be enrolled as a pilot study for the following patient populations: healthy, BI, SCI and amputation. The estimated number of total patients will be calculated based on our pilot study with 5 subjects for each group. Patient subjects will be screened at the outpatient clinic of TIRR Memorial Hermann Hospital. Subjects will be recruited and enrolled in the project if they meet the inclusion and exclusion criteria (see subject population).

The interventions/Experimental procedures

The experiment consists of 3 sessions, including 1) BreESTim + Sham tDCS (i.e., BreESTim only), 2) BreESTim +active tDCS, and 3) tDCS only. Three sessions will be conducted on three different days with an interval of at least 24 hours. In each session, a conditioning tDCS (active or sham) will be performed first, then followed by BreESTim.

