Anodal tDCS targeting M1 (Boggio et al. 2008) will be used. During each session, subjects will receive either active or sham stimulation to M1. A pair of surface sponge electrodes (35cm^2) will be soaked in saline and applied to the scalp. The anode electrode will be placed over C3 according to the 10-20 system for EEG electrode placement. The reference cathode electrode will be placed over the supraorbital area on the opposite side. For all active tDCS conditions, DC will be delivered by a specially developed, battery-driven, constant current stimulator

(Soterix Medical, NY) with a maximum output of 10mA. A constant current of 2 mA will be applied for 15 min (the effect is usually expected to last 1-2 hours after tDCS) (Boggio et al. 2008). After the 15-min tDCS (active or sham), BreESTim will follow immediately.

Figure 1 The experimental setup with BreESTim

The same BreESTim protocol (Li et al. 2013) will be used. Briefly, subjects will wear

facemask that will be connected to a Pneumotach system to record breathing signals. Surface electrodes will be trimmed to be applied to acupuncture points (Neiguan and Weiguan) (see Figure for experimental settings). In the BreESTim treatment, a single-pulse (0.1 ms square wave) electrical stimulation is delivered to

acupuncture points when subjects are taking a fast, strong, and deep inhalation, similar to a deep breath but faster and stronger. It is important to mention that subjects control the intensity of electrical stimulation, to increase the intensity as tolerated gradually. Subjects will be explicitly instructed that aversiveness of painful stimulation is part of treatment protocol. To standardize, the total number of electrical stimuli is 200. Sufficient rest time will be allowed during the treatment. The BreESTim treatment takes about 30 minutes.

The above intervention will be applied to the following subject populations:

Experiment 1: the effect of combined BreESTim and tDCS treatment in healthy subjects

Experiment 2: the effect of combined BreESTim and tDCS treatment on neuropathic phantom pain in amputation subjects

Experiment 3: the effect of combined BreESTim and tDCS treatment on neuropathic pain in SCI subjects

Experiment 4: the effect of combined BreESTim and tDCS treatment on neuropathic pain in BI subjects

Specimens:

No specimens will be collected

5. Subject Population

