In experiments 1-4, **5** subjects for each population (healthy, SCI, BI, and amputation) will be recruited and tested. An estimated number of patients will be obtained after the pilot study.

In experiment 1, healthy subjects will be recruited from residents, staff, therapists at TIRR Memorial Hermann in response to the flyer. The following inclusion/exclusion criteria will be followed (1) age between 18 and 60 years, (2) no clinically significant or unstable medical, neuropsychiatric, or chronic pain disorder, (3) no history of substance abuse or dependence, (4) no use of central nervous system-effective medication, (5) no history of brain surgery, tumor, pacemaker, or intracranial metal implantation or atrial fibrillation.

Patient subjects will be recruited from the TIRR outpatient clinic for experiments 2-4 for a total of 15 subjects.

Inclusion criteria: A patient who 1) has neuropathic pain after traumatic spinal cord injury or amputation or brain injury; 2) has chronic pain, >3 months; 3) is between 18 to 75 years of age; 4) is stable on oral pain medications at least two weeks. Patients are allowed to continue their pain medications, i.e., no change in pain medications.

Exclusion criteria: Patients will be excluded if they 1) are currently adjusting oral pain medications for their neuropathic pain; 2) have pain, but not neuropathic, e.g., from inflammation at the incision wound of the residual limb

or neuroma; 3) have a pacemaker in order to avoid possible side effects of electrical stimulation; 4) have amputation in their arm(s); 5) have SCI involving impairment of arms; 6) are not able to follow commands, or to give consent; 7) have asthma or other pulmonary disease; 8) are not medically stable; 9) have preexisting psychiatric disorders; 10) alcohol or drug abuse.

6. Data Analysis

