The risks associated with this study are minimal. Electrical stimulation has been used extensively in clinical settings. Patients may feel uncomfortable, or even painful during electrical stimulation. The patients will be specifically instructed that they are encouraged to increase the intensity of electrical stimulation to the level they may feel uncomfortable, but they need to be able to tolerate at that level if given repetitively. They are also explicitly instructed to decrease the intensity of electrical stimulation if they cannot tolerate it. Surface electrodes can cause skin irritation from the tape adhesive or the electrode paste. Breathing through a face mask may be make patients feel uncomfortable. All tested subjects in the previous studies (approximately 70 subjects, including patients) tolerated the mask well.

All the tDCS safety papers ([poreisz 2007](#)-

<http://www.ncbi.nlm.nih.gov/pubmed/17452283>, [kessler 2011](#)-

<http://www.ncbi.nlm.nih.gov/pubmed/22037128> , [nitsche 2003](#)-

<http://www.ncbi.nlm.nih.gov/pubmed/14580622>) point to adverse effects as

itching/tingling. Over 600 studies have published using tDCS and Soterix units operate within the established current intensities/durations (0-2 mA, 10-40 min).

8. Benefits:

There are several potential benefits in this study: 1) direct benefit to subjects as their neuropathic pain may be relieved by the intervention; 2) benefit to the class of subjects: other patients in the same patient population may be benefit if the intervention is applied to them; 3) adding to the knowledge base: the findings will be definitely added to the knowledge base. Specifically, the study will provide evidence of an alternative and innovative intervention for neuropathic pain management.

9. Risk-benefit Ratio:

In view of the minimal risk, benefits and the knowledge to be gained far outweigh the risks.

10. Consent Procedures:

Informed consent will be obtained from the subject at the Motor Recovery Laboratory (B-107) at TIRR Memorial Hermann. After a subject is identified and interested in participating, informed, written consent will be obtained by the study coordinator.

11. Confidentiality Procedures:

In order to minimize risk to confidentiality, all data will be de-identified, coded with a study specific identification number, maintained on a password-protected server, and/or kept in a locked office. No findings will be released without written authorization by the subject.

12. Costs:

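### Intracranial metal bars healthy volunteers but not patients, so a medically stable brain-injury patient with intracranial metal can receive two active 2 mA tDCS sessions

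*Combined protocol and SAP*

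**What the plan says.** Section 5 (Subject Population) contains two eligibility lists. The list for healthy subjects is introduced as applying to experiment 1, and its fifth item requires "no history of brain surgery, tumor, pacemaker, or intracranial metal implantation or atrial fibrillation". The list for patients covers experiments 2 to 4 (15 subjects: 5 amputation, 5 SCI, 5 brain injury) and has ten exclusions. The only device it names is in item 3, which excludes patients who "have a pacemaker in order to avoid possible side effects of electrical stimulation". The broadest medical item, number 8, excludes those who "are not medically stable".

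Section 4 (The interventions/Experimental procedures) gives each subject three sessions: BreESTim with sham tDCS, then "2) BreESTim +active tDCS, and 3) tDCS only". It has one tDCS description. "The anode electrode will be placed over C3 according to the 10-20 system for EEG electrode placement", the cathode goes over the opposite supraorbital area, and "A constant current of 2 mA will be applied for 15 min". It then says: "The above intervention will be applied to the following subject populations". Experiment 4, in brain injury, is on the list that follows.

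Section 7 (Potential Risks/Discomforts) opens with "The risks associated with this study are minimal". For tDCS it names itching and tingling, and says the units stay within established limits of 0-2 mA and 10-40 minutes. It does not mention implants.

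**The concern.** The sponsor keeps people with intracranial metal out of the healthy group before passing current across the scalp. It then gives the same current, through the same montage, to patients who are not screened for it. One of those groups is defined by brain injury, where intracranial metal is more plausible than among staff volunteers. The stricter rule therefore sits with the group less likely to need it, and no reason for the difference is given.

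What is at stake is patient safety, judged against the protocol's own eligibility rules. A coordinator who follows section 5 exactly would enrol and stimulate such a patient, in a study whose risk section calls the risk minimal and does not consider implants.

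**Working it through.** The plan states no figure on this point, so there is none to reproduce. The check compares the two lists, counts the exposure, and then sizes it under an assumption.

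**1. Eligibility lists (section 5).**

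| Item | Healthy (experiment 1) | Patients (experiments 2-4) |
|---|---|---|
| Pacemaker | excluded | excluded |
| Intracranial metal | excluded | not mentioned |
| Brain surgery, tumor | excluded | not mentioned |
| Atrial fibrillation | excluded | not mentioned |

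Intracranial metal appears in 1 of 5 healthy criteria and 0 of 10 patient exclusions. The other patient exclusions concern medication changes, non-neuropathic pain, arm amputation, SCI with arm impairment, ability to follow commands or consent, pulmonary disease, medical stability, psychiatric disorder, and alcohol or drug abuse. None of these covers a stable outpatient with metal in the head.

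**2. Active sessions per subject (section 4).** There are 3 sessions and only the first is labelled sham, so 3 - 1 = 2 are active. The tDCS-only session does not carry the word active. Section 6 analyses it as an intervention level of its own, and section 4 speaks of active tDCS conditions in the plural, so active is the sound reading.

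**3. Dose.** 2 sessions x 15 min = 30 min at 2 mA per subject. For the brain-injury group, 5 subjects x 2 = 10 active sessions. That is the ceiling, reached only if all five have metal. With k such subjects the number is 2k.

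**4. Chance of enrolling at least one such subject.** Let p be the proportion of otherwise eligible brain-injury candidates with intracranial metal. The documents do not give p; 5% to 30% is an assumption. Treating the 5 subjects as independent:

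- P(at least one of 5) = 1 - (1 - p)^5
- Expected active sessions in subjects with metal = 10p
- Candidates needed to fill 5 places if metal is excluded = 5/(1 - p)

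| p (assumed) | P(at least one of 5) | Expected sessions | Candidates needed |
|---|---|---|---|
| 5% | 1 - 0.95^5 = 22.6% | 0.5 | 5.26 |
| 10% | 1 - 0.90^5 = 41.0% | 1.0 | 5.56 |
| 20% | 1 - 0.80^5 = 67.2% | 2.0 | 6.25 |
| 30% | 1 - 0.70^5 = 83.2% | 3.0 | 7.14 |

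**The case against.** The strongest reply is that the safety purpose of the healthy criterion is inferred. Section 5 gives no reason for it, and the healthy list also bars chronic pain and CNS-active medication, which could not sensibly carry over to patients. It could be read as defining a neurologically normal sample. The one exclusion with a written safety reason, the pacemaker, does apply to patients. It is true that the rationale is not stated. But metal stands beside the pacemaker in the same healthy criterion, and the reason given for the patient pacemaker exclusion is side effects of electrical stimulation. That reason reaches intracranial metal far more readily than it reaches, say, tumor. A wish to keep brain-injury patients with past surgery eligible could explain dropping surgery and tumor. It does not explain dropping metal, and it does not apply to the SCI and amputation groups.

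Three further points stand in part.

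- **Size.** The documents do not say what 2 mA would do in someone with intracranial metal, and the prevalence range is assumed and wide. The percentages measure exposure, not harm, and should not be used to argue severity.
- **Number of active sessions.** Two is a reading, and section 4 also says that tDCS is followed by BreESTim in each session, which sits badly with a tDCS-only session. One active session is certain, and two is what the design and analysis require.
- **What cannot be seen.** The consent pages and the published tDCS protocol being adopted are not available, so screening in practice may be better than the written list. What is established is a gap in the written patient criteria, which are the ones that control enrolment.

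**Conclusion.** The concern holds. As written, section 5 makes a medically stable brain-injury patient with intracranial metal eligible if the other criteria are met, and section 4 gives that patient two active sessions, 30 minutes in total at 2 mA. This follows from the text and needs no outside figure. It rests on two readings: that the tDCS-only session is active, and that metal is excluded in healthy subjects at least partly for safety.

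How many subjects are affected is unknown. Under the assumed 5% to 30%, the chance of at least one among the 5 brain-injury subjects is 23% to 83%, with 0.5 to 3 active sessions expected in such subjects. One would be enough to justify the change. The sponsor should make it: the gap bears on patient safety, and closing it is cheap.

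**What to change.** In section 5, extend patient exclusion 3 so that it names *intracranial metal implantation* alongside the pacemaker, under the reason already given there, and check it at the outpatient screening before enrolment. Say whether skull plates and retained metal fragments count, since a fragment is not strictly an implantation.

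Do not make prior brain surgery or tumor outright exclusions for patients, because that could remove part of the experiment 4 population. Have the investigator treat such a history as the prompt to check for metal. If the sponsor means to admit patients with intracranial metal, section 5 should say so and section 7 should address the risk.

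The cost is a few words, one check at screening and possibly slower recruitment. Under the same assumed range, about 5.3 to 7.1 otherwise eligible brain-injury candidates would be needed to fill 5 places, instead of 5.

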Pre-intervention and post-intervention measurements include electrical sensation and pain thresholds and warm sensation and heat pain thresholds as used in our recent study (Li et al. 2013). In addition, visual analogue scores (VAS), modified visual analogue scores (mVAS) will be recorded in patient subjects. These measurements will be taken pre- and post-intervention for both sessions. VAS has been extensively used and validated (McCarthy et al. 2005). mVAS further quantifies the effect of pain reduction by measuring duration and amount of change in VAS, i.e., how much pain was reduced and how long it lasted (reduction × hours). It is necessary to note that pain rating is very subjective. This cross-over design uses subjects as their own control.

Heart rate variability as objective outcome measurements

We have been searching for non-invasive objective pain outcome assessment. Heart rate variability has recently recognized a physiological marker for pain assessment (Cowen et al. 2015), see also Appelhans & Leucken 2008 (both articles are uploaded to the iRIS).

We propose to add 5 minutes of Heart Rate recordings before and after the interventions. Experimental procedures and data analysis will be adopted from the above articles.

Two-way repeated measures ANOVA with factors INTERVENTIONS (3 levels, BreESTim only, tDCS only and tDCS+BreESTim) and TIME (pre- and post-intervention) will be used determined statistical significance for each threshold (electrical sensation and pain thresholds, and thermal sensation and pain threshold, mVAS). It is expected that BreESTim + tDCS will have better analgesic effect than BreESTim or tDCS alone.

7. Potential Risks/Discomforts:

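### Patient exclusion 3 is meant to avoid side effects of electrical stimulation but names only a pacemaker, so the written criteria admit a medically stable patient with another active implanted electronic device

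*Combined protocol and SAP*

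**What the plan says.** Section 5 (Subject Population) has two separate eligibility lists, one for the healthy subjects of experiment 1 and one for the patients of experiments 2-4. On the size of the patient part it says: "Patient subjects will be recruited from the TIRR outpatient clinic for experiments 2-4 for a total of 15 subjects".

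The third patient exclusion applies to those who "have a pacemaker in order to avoid possible side effects of electrical stimulation". It is the only patient criterion about a device. The healthy list is broader on implants; its criterion 5 requires "no history of brain surgery, tumor, pacemaker, or intracranial metal implantation or atrial fibrillation".

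Section 4 (Description of Study, Subject recruitment) makes entry depend on these lists: "Subjects will be recruited and enrolled in the project if they meet the inclusion and exclusion criteria".

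Patients are stimulated at two sites. For active tDCS, section 4 says: "A constant current of 2 mA will be applied for 15 min". The anode is over C3 and the cathode is above the opposite eye. For BreESTim, given through surface electrodes at acupuncture points, it says: "To standardize, the total number of electrical stimuli is 200". Section 6 adds electrical testing as an outcome: "Pre-intervention and post-intervention measurements include electrical sensation and pain thresholds".

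**The concern.** Exclusion 3 states its purpose as well as its rule, and the two do not have the same scope. The purpose is to avoid unwanted effects of electrical stimulation. The rule covers one kind of device. A screener who applies the list as written has no device-based ground for turning away a patient with a different active implant, even where the stated purpose would suggest at least asking about it.

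The devices in question are not remote from this setting. The patients have chronic neuropathic pain after spinal cord injury, brain injury or amputation, and section 2 (Background) itself lists spinal cord stimulation and deep brain stimulation among neurostimulation techniques when it introduces tDCS for pain management. That gives no frequency, but it makes the question a natural one at screening.

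What is at stake is patient safety and consistent screening. The point does not touch the crossover comparison, the type I error or the power.

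**Working it through.** No probability calculation applies, because the documents give no device frequency and no rate of harm. The check is a count and an item-by-item reading.

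**Number of subjects covered.** Section 4 plans 5 subjects in each of 4 groups: 4 × 5 = 20. Three groups are patients (SCI, BI, amputation): 3 × 5 = 15. This matches the 15 stated in section 5. The patient list therefore governs 15 of 20 subjects.

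**Number of criteria.** The patient list has 4 inclusion and 10 exclusion items: 4 + 10 = 14. Leaving out exclusion 3, there are 14 − 1 = 13.

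**Does any of the 13 catch a device other than a pacemaker?**

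| Item | Subject matter | Names a device? |
|---|---|---|
| Inclusion 1 | Neuropathic pain from one of the three conditions | No |
| Inclusion 2 | Pain for more than 3 months | No |
| Inclusion 3 | Age 18 to 75 | No |
| Inclusion 4 | Stable oral pain medication | No |
| Exclusion 1 | Oral pain medication being adjusted | No |
| Exclusion 2 | Pain that is not neuropathic | No |
| Exclusion 4 | Arm amputation | No |
| Exclusion 5 | Arm impairment from SCI | No |
| Exclusion 6 | Cannot follow commands or consent | No |
| Exclusion 7 | Pulmonary disease | No |
| Exclusion 8 | Medically unstable | No |
| Exclusion 9 | Psychiatric disorder | No |
| Exclusion 10 | Alcohol or drug abuse | No |

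Some items could remove a device user incidentally, for instance through a psychiatric history, but none does so because of the device.

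**Test case.** Take a patient with a traumatic spinal cord injury, unimpaired arms, neuropathic pain for more than 3 months, stable oral medication and a spinal cord stimulator, who is medically stable and has none of the other excluded conditions. All 4 inclusion items are met and none of the 10 exclusions applies. Under the enrolment rule in section 4 this patient is eligible. A brain-injury patient with a deep brain stimulator passes in the same way.

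**Does another section fill the gap?** Section 7 (Potential Risks/Discomforts) discusses discomfort, skin irritation, the face mask, and itching or tingling from tDCS. Its safeguard is that patients lower the stimulation intensity when they cannot tolerate it. That protects against discomfort and does not screen for devices, and the active tDCS current is fixed at 2 mA. Section 7 contains no device screening.

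**Is the healthy list open in the same way?** Largely not. Healthy criterion 5 bars brain surgery and intracranial metal, which would cover a deep brain stimulator. Healthy criterion 2 bars clinically significant medical, neuropsychiatric or chronic pain disorders, which would ordinarily cover the conditions for which a defibrillator or spinal cord stimulator is implanted.

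**The case against.** The strongest objection is that the hazard is not in the documents. The side-effect reason is given for pacemakers only. No section says that a defibrillator or a neurostimulator is at risk under these currents, and section 2 mentions spinal cord and deep brain stimulation as pain techniques, not as contraindications. This stands. The extension to other devices is an inference from the criterion's own reason and should be presented as one. A reader might infer that these devices share the pacemaker's risk and differ from it only in type; nothing in the documents supports that equivalence.

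Second, screening takes place at one outpatient clinic, and the medical-stability exclusion leaves room for clinical judgement. This stands in part. Judgement may well catch such a patient, but the item does not mention devices, and a stable device user is not medically unstable.

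Third, pacemaker might be read to include a defibrillator. That is possible, and it weakens the defibrillator example. It hardly reaches a spinal cord or deep brain stimulator.

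Fourth, a reader might treat the amount of stimulation each patient receives as the size of the problem. It is not: the schedule is the same for subjects with and without a device, so it says nothing about how likely or how serious the gap is.

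Fifth, the contrast between the two lists on brain surgery and intracranial metal is better documented, since the protocol itself applies those bars to healthy subjects only. That is true, but it is a separate point. Carrying those items across would cover a deep brain stimulator and would not name a spinal cord stimulator or a defibrillator.

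**Conclusion.** The point holds as a low-severity precaution. The written criteria for 15 of 20 subjects would admit a medically stable patient with an active implanted electronic device other than a pacemaker, and that patient would receive both scalp direct current and peripheral pulses.

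This rests on three assumptions: that the criteria are applied as written; that pacemaker carries its ordinary meaning; and that no device criterion stands elsewhere. On the last, part of the text before section 4 was not in the copy read, but eligibility is set out in section 5, to which section 4 refers the reader.

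The documents do not support going further. They report no device harm and section 7 calls the risks minimal, so this is not a demonstrated hazard. They give no device frequency, so the chance that any of the 15 patients has such a device is unknown. There is no basis for claiming bias in the treatment comparison.

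**What to change.** In section 5, reword patient exclusion 3 so that after pacemaker it reads: *or any other active implanted electronic device (e.g. defibrillator, spinal cord or deep brain stimulator)*. Keep the stated reason as it is.

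The cost is one line of text and one screening question. Some otherwise eligible patients may be lost; the documents do not allow the number to be estimated, so it should not be assumed to be negligible. No change to the healthy-subject criteria is needed, and the analysis and sample size are unaffected.

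### No common post-measurement time is set, so on the natural reading the tDCS-only session is measured about 30 minutes earlier after tDCS than the combined session

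*Combined protocol and SAP*

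**What the plan says.** Section 4 (The interventions/Experimental procedures) lists three sessions per subject: "1) BreESTim + Sham tDCS (i.e., BreESTim only), 2) BreESTim +active tDCS, and 3) tDCS only". It then gives the order within a session: "In each session, a conditioning tDCS (active or sham) will be performed first, then followed by BreESTim". That sentence does not fit a session of tDCS only.

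The same section gives the durations. For tDCS: "A constant current of 2 mA will be applied for 15 min", with the remark that "the effect is usually expected to last 1-2 hours after tDCS". There is no gap before the second treatment: "After the 15-min tDCS (active or sham), BreESTim will follow immediately". For its length: "The BreESTim treatment takes about 30 minutes". Rest is allowed within that treatment.

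Section 6 (Data Analysis) sets the measurement times in one sentence: "These measurements will be taken pre- and post-intervention for both sessions". The analysis is a repeated measures ANOVA with three interventions crossed with a pre/post factor. It is named for the thresholds and mVAS, and has no term for minutes since tDCS. The expected result is that the combination does better than either component alone.

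**The concern.** The hypothesis has two halves: the combination against BreESTim alone, and the combination against tDCS alone. Sham tDCS puts the first pair on the same timeline. Nothing described in the plan does so for the second pair. The tDCS-only session has no sham BreESTim and no stated wait, so its intervention ends about 30 minutes sooner.

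If staff measure when the intervention ends, the two sessions are read at different points of a short-lived tDCS effect, and with different intervals between the two tests. The difference goes with the treatment. Randomising session order therefore does not remove it, and neither does using subjects as their own controls. A difference between the sessions, or the lack of one, could not be separated from the difference in timing. The pilot is also meant to supply the sample size for later work, so a distorted contrast could carry forward.

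**Working it through.** The plan states no figure for this point, so there is none to reproduce. The check is timeline arithmetic.

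**Inputs (section 4).** tDCS lasts 15 min. BreESTim follows with no gap and takes about 30 min. The tDCS effect is expected to last 1-2 hours, that is 60-120 min.

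**Assumptions.** Session 3 contains no BreESTim. Pre measurements are taken just before tDCS starts, and post measurements when that session's intervention ends. Time spent on the tests themselves is ignored.

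**Step 1: timeline.**

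| Session | Post, min after tDCS start | Post, min after tDCS end |
|---|---|---|
| tDCS only | 15 | 0 |
| BreESTim + active tDCS | 15 + 30 = about 45 | about 30 |
| BreESTim + sham tDCS | 15 + 30 = about 45 | about 30 (sham) |

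**Step 2: what each contrast estimates.** Write T(m) for the tDCS effect m minutes after stimulation ends, B for the effect of the BreESTim procedure, and d(g) for drift over a pre-to-post gap of g minutes. Assume that these add.

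- tDCS only: T(0) + d(15)
- Combined: T(30) + B + d(45)
- BreESTim only: B + d(45)
- Combined minus tDCS only = B + [T(30) − T(0)] + [d(45) − d(15)]
- Combined minus BreESTim only = T(30)

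Both bracketed terms come from timing alone. The pre/post factor in the ANOVA cannot estimate them, because minutes since tDCS are fixed by the session. The second contrast has no such term.

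**Step 3: possible size of T(30) relative to T(0).** The plan gives a duration but no shape, so each line below rests on an assumed curve.

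- Linear decline to zero: 1 − 30/60 = 0.50 for a 1-hour effect, and 1 − 30/120 = 0.75 for a 2-hour effect. So 50-75% remains.
- Exponential decline with 5% left at the end of the window: 0.05^(30/60) = 0.22 and 0.05^(30/120) = 0.47. So 22-47% remains.
- Plateau through the first 30 minutes: about 100% remains, and T(30) − T(0) is about 0.
- An effect that builds after stimulation: above 100%, which favours the combination.

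The drift term can have either sign, and the documents give nothing to size it.

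**Step 4: after the fix.** With about 30 minutes of rest before the post tests, tDCS only becomes T(30) + d(45). Combined minus tDCS only is then B, and the timing gap falls from about 30 to 0 min.

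**Step 5: outcomes.** Thresholds, VAS and the heart rate recording are readings at one occasion and are exposed. The plan defines mVAS as the amount of pain reduction multiplied by its duration in hours. It covers a period, so the fractions in step 3 do not carry over to it.

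**The case against.** The strongest reply is that the plan does not say when the tDCS-only measurement is taken. A reader might infer that it is scheduled right after tDCS, but no sentence says so. The order sentence ("In each session, a conditioning tDCS (active or sham) will be performed first, then followed by BreESTim") leaves that session's timeline unclear. A matched wait may be intended, or may be set out in the published protocols that the plan adopts, or in a figure or background text not available for this review. This stands, and it is why the point is conditional. It does not remove the point: the measurement section gives no common time, so staff could follow either schedule or vary it.

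Four further limits stand:

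- A reader might put the gaps at 30 and 45 minutes at least, counting rest on top of BreESTim. Rest is allowed during that treatment, so it is naturally part of the 30 minutes. The plan supports about 30 and about 45.
- A reader might take the linear calculation to mean that a handicap of 25-50% of the tDCS effect is built in. That depends on an assumed curve; a plateau fits the plan's statement equally well and gives about 0%.
- A reader might take the reference to two sessions to mean that one of the three is not measured. The three-level ANOVA shows that all three are meant to be. It is a slip of wording.
- This is a pilot with 5 subjects per group, and half of the hypothesis is untouched. That lowers the severity, but it is no reason to keep an avoidable timing difference.

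**Conclusion.** The concern holds in conditional form. The plan sets no common post-measurement time and describes nothing to fill the BreESTim period in the tDCS-only session. If post measurements follow the end of each session's intervention, which is the natural reading, the tDCS-only reading falls about 30 minutes earlier after tDCS than the combined one, and the pre-to-post gap is about 15 against about 45 minutes. The combined-versus-tDCS-only contrast for thresholds, VAS and heart rate is then confounded with both.

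The documents do not support a stated size or direction. A fading tDCS effect would work against the combination; a building effect, or drift over a longer sitting, could favour it. They also do not support extending the point to combined versus BreESTim-only, or applying it with the same force to mVAS.

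This should be fixed. It does not by itself undermine the pilot. Confidence is medium, because the timing is inferred.

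**What to change.** In section 6, state that in all three sessions post-intervention measurements start at the same time after the end of tDCS. In the tDCS-only session, add a rest period of about BreESTim length (about 30 minutes) before the post tests. Log the actual minutes from the end of tDCS to each test.

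In the same amendment, change the reference to two sessions so that it covers all three. Also reconcile the section 4 sentence that has BreESTim follow in every session with the listing of "2) BreESTim +active tDCS, and 3) tDCS only".

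The cost is about 30 minutes of sitting in one of three sessions and a short amendment. The change equalises timing only. It does not balance expectation, or the non-specific effects of the mask, the forced breathing and the painful stimulation, so a remaining difference should not be credited to BreESTim's specific action on this ground alone.
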